### **Online Patient Education (PE) Control Group**

The online PE program provides static information about: insomnia symptoms; the impact, prevalence, and causes of insomnia; when to see a doctor; and basic lifestyle, environmental, and behavioral strategies to improve sleep. The content for this program was informed based on a review of insomnia-focused websites at the time of development. In some areas, content between the PE and SHUTi web programs overlap; however, SHUTi differs from the PE website in important ways. In contrast to SHUTi, the PE website (1) does not personalize or individually tailor treatment recommendations based on user input; (2) presents content in a simple, static form, without interactive assessments; and (3) delivers content all at once, meaning the user can access full site content immediately, rather than having to wait for content to be metered, or unlocked, over time. The participant will have 9 weeks to review the patient education website and at week 10 will be asked to complete post-assessment questionnaires/sleep diaries and complete the remote evaluation for post intervention assessments.

## **5.0 REQUIRED EVALUATIONS, TESTS, AND OBSERVATIONS**

### **5.1. Pre-Study Evaluations**

A recruitment mailing will be sent intermittently by the CCSS team to determine interest in the study. Screening questions must be completed online via DatStat to determine study eligibility.

### **5.2. Evaluations During Study**

There are 3 assessment time points during the study: baseline (pre-intervention), post-intervention, and 6-month follow-up. At each time point, participants will complete a remote cognitive evaluation, give a blood sample using the dried

St. Jude Children's Research Hospital

IRB NUMBER: 19-0121

IRB APPROVAL DATE: 05/04/2021

blood spot (DBS) method, wear a WHOOP wrist monitor for 7 to 11 consecutive days. Participants in the study will be asked to complete questionnaires and sleep diaries at each of these time points. All assessments will be completed remotely and study materials (DBS kits, WHOOP wrist monitors, instruction guide, charging cables) will be mailed to the participant. Prior to mailing the equipment to the study participant, all equipment will be sanitized with a product from the list of Approved Disinfectants & Cleaners available on the COVID-19 Disinfectant Guide. The appropriate contact time specific to the disinfectant will be used. We plan to use PDI Sani-Cloth® with a contact time of 2 minute but if unavailable only approved disinfectants and cleaners from the list provided by St. Jude will be used. The sanitized equipment will be packed by a study team member wearing a mask and gloves. Packages will be sent via non-contact drop-off. These measures will minimize exposure to other team members and ensure social-distancing guidelines are met for study staff. Upon return, the package with the equipment will sit for 24 hours before being opened. The study team member will wear gloves and a mask when unpacking the box. All equipment will be sanitized upon return using a product from the list of Approved Disinfectants & Cleaners available on the COVID-19 Disinfectant Guide. The appropriate contact time specific to the disinfectant will be used.

## REQUIRED EVALUATIONS & OBSERVATIONS

Study Procedure	Time Point		
	Baseline	Post-Intervention	6 Month Follow-Up
Dried Blood Spot collection (DBS)	X	X	X
CNS Vital Signs remote cognitive assessment	X	X	X
Insomnia Severity Index (ISI)	X	X	X
Drug Abuse Screen Test (DAST-10)	X		
Alcohol Use Disorders Identification Test (AUDIT)	X		
FACIT-Fatigue Questionnaire	X	X	X
Epworth Sleepiness Scale (ESS)	X	X	X
Childhood Cancer Neurocognitive Questionnaire (CCSS-NCQ)	X	X	X
Patient Health Questionnaire (PHQ-9)	X	X	X
Generalized Anxiety Disorder (GAD-7)	X	X	X
WHOOP wrist monitor	X	X	X
Health-related Quality of Life Questionnaire	X	X	X
PROMIS Global Health	X	X	X

Sleep Diary	X	X	X
Work Productivity and Activity Impairment Questionnaire (WPAI)	X	X	X
Work and Social Adjustment Scale (WSAS)	X	X	X

## 6.0 CRITERIA FOR REMOVAL FROM PROTOCOL

### 6.1. Off Study Criteria

- 6.1.1. All protocol interventions are complete
- 6.1.2. Death
- 6.1.3. Lost to follow-up
- 6.1.4. Request of the Patient/Parent
- 6.1.5. Discretion of the Study PI, such as the following
  - The researcher decides that continuing in the study would be harmful
  - The participant misses so many appointments that the data cannot be used in the study
  - The participant's condition gets worse
  - New information is learned that the study is not in the participant's best interest

## 7.0 SAFETY AND ADVERSE EVENT REPORTING REQUIREMENTS

### 7.1. Reporting Adverse Experiences and Deaths to St. Jude IRB

7.1.1. Only “unanticipated problems involving risks to participants or others” referred to hereafter as “unanticipated problems” are required to be reported to the St. Jude IRB promptly, but in no event later than 10 working days after the investigator first learns of the unanticipated problem. Regardless of whether the event is internal or external (for example, an IND safety report by the sponsor pursuant to 21 CFR 312.32), only adverse events that constitute unanticipated problems are reportable to the St. Jude IRB. As further described in the definition of unanticipated problem, this includes any event that in the PI’s opinion was:

- Unexpected (in terms of nature, severity, or frequency) given (1) the research procedures that are described in the protocol-related documents, such as the IRB-approved research protocol and informed consent document, as well as other relevant information

available about the research; (2) the observed rate of occurrence (compared to a credible baseline for comparison); and (3) the characteristics of the subject population being studied; and

- Related or possibly related to participation in the research; and
- Serious; or if not serious suggests that the research places subjects or others at a greater risk of harm (including physical, psychological, economic, or social harm) than was previously known or recognized.

Unrelated, expected deaths do not require reporting to the IRB. Though death is “serious”, the event must meet the other two requirements of “related or possibly related” and “unexpected/unanticipated” to be considered reportable.

Deaths meeting reporting requirements are to be reported immediately to the St. Jude IRB, but in no event later than 48 hours after the investigator first learns of the death.

7.1.2. The following definitions apply with respect to reporting adverse experiences:

7.1.2.1. **Serious Adverse Event:** Any adverse event temporally associated with the subject’s participation in research that meets any of the following criteria:

- results in death;
- is life-threatening (places the subject at immediate risk of death from the event as it occurred);
- requires inpatient hospitalization or prolongation of existing hospitalization;
- results in a persistent or significant disability/incapacity;
- results in a congenital anomaly/birth defect; or
- any other adverse event that, based upon appropriate medical judgment, may jeopardize the subject’s health and may require medical or surgical intervention to prevent one of the other outcomes listed in this definition (examples of such events include: any substantial disruption of the ability to conduct normal life functions, allergic bronchospasm requiring intensive treatment in the emergency room or at home, blood dyscrasias or convulsions that do not result in inpatient hospitalization, or the development of drug dependency or drug abuse), a congenital anomaly/birth defect, secondary or concurrent cancer, medication overdose, or is any medical

event which requires treatment to prevent any of the medical outcomes previously listed.

7.1.2.2. **Unexpected Adverse Event:**

- Any adverse event for which the specificity or severity is not consistent with the protocol-related documents, including the applicable investigator brochure, IRB approved consent form, Investigational New Drug (IND) or Investigational Device Exemption (IDE) application, or other relevant sources of information, such as product labeling and package inserts; or if it does appear in such documents, an event in which the specificity, severity or duration is not consistent with the risk information included therein; or
- The observed rate of occurrence is a clinically significant increase in the expected rate (based on a credible baseline rate for comparison); or
- The occurrence is not consistent with the expected natural progression of any underlying disease, disorder, or condition of the subject(s) experiencing the adverse event and the subject's predisposing risk factor profile for the adverse event.

7.1.2.3. **Internal Events:** Events experienced by a research participant enrolled at a site under the jurisdiction of St. Jude IRB for either multicenter or single-center research projects.

7.1.2.4. **External Events:** Events experienced by participants enrolled at a site external to the jurisdiction of the St. Jude Institutional Review Board (IRB) or in a study for which St. Jude is not the coordinating center or the IRB of record.

7.1.2.5. **Unanticipated Problem Involving Risks to Subjects or Others:** An unanticipated problem involving risks to subjects or others is an event which was not expected to occur and which increases the degree of risk posed to research participants. Such events, in general, meet all of the following criteria:

- unexpected;
- related or possibly related to participation in the research; and
- suggests that the research places subjects or others at a greater risk of harm (including physical, psychological, economic, or social harm) than was previously known or recognized. An unanticipated problem involving risk to subjects or others may exist even when actual harm does not occur.

7.1.3. Consistent with FDA and OHRP guidance on reporting unanticipated problems and adverse events to IRBs, the St. Jude IRB does not require the submission of external events, for example IND safety reports, nor is a summary of such events/reports required; however, if an event giving rise to an IND safety or other external event report constitutes an “unanticipated problem involving risks to subjects or others” it must be reported in accordance with this policy. In general, to be reportable external events need to have implications for the conduct of the study (for example, requiring a significant and usually safety-related change in the protocol and/or informed consent form).

7.1.4. Although some adverse events will qualify as unanticipated problems involving risks to subjects or others, some will not; and there may be other unanticipated problems that go beyond the definitions of serious and/or unexpected adverse events. Examples of unanticipated problems involving risks to subjects or others include:

- Improperly staging a participant’s tumor resulting in the participant being assigned to an incorrect arm of the research study;
- The theft of a research computer containing confidential subject information (breach of confidentiality); and
- The contamination of a study drug. Unanticipated problems generally will warrant consideration of substantive changes in the research protocol or informed consent process/document or other corrective actions in order to protect the safety, welfare, or rights of subjects or others.

## **8.0 DATA COLLECTION, STUDY MONITORING, AND CONFIDENTIALITY**

### **8.1. Data Collection**

Data collection will be accomplished using online data collection tools DatStat Connect, WHOOP Platform, CNS Vital Signs and RICE. DatStat Connect has been utilized by the CCSS for consenting and online data collection. The RICE Platform includes capabilities for contacting participants, providing access to instructional and demonstration videos, collecting data and secure transmission of data to the study team. The RICE Platform allows for input constraints in the tools as well as real-time validation of data formats and ranges, providing real-time feedback to the user if “out-of-range” values are recorded. WHOOP Platform is a secure cloud-based platform hosted by WHOOP that will be used by participants to transmit heart rate data and activity/sleep data using an app on their smart phone or tablet, to the WHOOP cloud. CNS Vital Signs platform will be used to collect data for the remote cognitive assessments. Data will be downloaded and saved in a secure database. To protect the confidentiality of the participants, only participant ID and year of birth will be used and no PHI will be sent to the CNS Vital Signs for the remote cognitive assessment.

### **8.2. Study Monitoring**

#### **Lowest Risk:**

This study is considered lowest risk for monitoring purposes. The Principal Investigator (PI) and study team are responsible for ensuring protocol and regulatory compliance. The St. Jude monitoring group will not monitor this study. The study team is responsible for data quality and will meet as needed to review case histories or quality summaries on participants and will generate minutes which are signed by the PI.

Protocol continuing reviews by the Institutional Review Board (IRB) and Scientific Review Committee (CT-SRC) will occur at least annually. In addition, Unanticipated Problems and/or Serious Adverse Event reports are reviewed by the IRB.

### **8.3. Confidentiality**

Study numbers will be used in place of an identifier such as a medical record number. No research participant names will be included in the final data set. The list containing the study number and participant name will be included in a secure database only accessible to the St. Jude study team.

The medical records of study participants may be reviewed by the St. Jude IRB, FDA, clinical research monitors, etc.

## 9.0 STATISTICAL CONSIDERATIONS

Anticipated Primary Completion Date: January 1, 2022
Anticipated Study Completion Date: July 1, 2023

### 9.1. Summary of Primary and Secondary Objectives

#### Statistical Analysis

A randomized controlled design will be employed for the proposed study. We plan to enroll a total of 352 survivors (176 of each sex), and assuming 10% drop out by the post-intervention 9-week assessment, we will have a total of 320 survivors (160 of each sex) remaining for evaluation. Balance of patient characteristics between study arms will be evaluated and if necessary, adjusted comparisons will be carried out.

The primary endpoint of the study will be the ISI measure of insomnia severity represented as described above. The difference in score from baseline to post-intervention (10 weeks) and baseline to 6 months post-intervention will be calculated and the mean of these differences compared between study arms using linear regression (adjusted for stratification factors). The primary time point of interest will be at 10 weeks, with a secondary endpoint evaluating maintenance at 6 months after intervention. Due to potential sex differences in insomnia and cognition, *a priori* we plan to carry out all analyses and report results separately by sex. Our study is not powered to detect meaningful interaction effects, but if we deem that the effects are reasonably comparable between sexes we will consider presenting combined analysis to increase precision of the estimate. Because this is a randomized trial we expect analyses to be simple and directed towards ascertaining controlled and generalizable intervention effects. The primary endpoint will be considered significant at the two-sided 0.05 level. Estimates of intervention effects (mean differences) will be presented along with associated confidence intervals and two-sided p-values.

Because mean scores do not reflect the number of survivors who have clinically significant insomnia symptoms, secondary analyses of sleep will compare the proportion of survivors who no longer meet the clinical criteria for insomnia (ISI  $\leq 7$ ) between study arms post-intervention (10 weeks) and at 6 months (noting that 100% of eligible participants will meet the criteria at randomization), using logistic regression models. Additional measures of sleep will also be summarized and compared (sleep diary, actigraphy, fatigue, daytime sleepiness) from baseline, post-intervention, and 6 months. Using the same analytic framework as above, we will evaluate the effect of study intervention on the secondary endpoints of neurocognitive impairment: patient reported (Task Efficiency, Memory, Emotional Regulation) and directly assessed (attention, memory, and executive function) with continuous outcome measures. Additional analyses relevant to secondary objectives focus on better understanding the associations and mediating relationships between the CBTi intervention, insomnia, neurocognition, emotional distress, cardiovascular risk indices and HRQoL (see Figure 2 for theoretical framework).

direct relationships between change in ISI (baseline to post-intervention) with emotional distress and cardiac health indices at postintervention time points and with HRQoL measures. To establish whether a mediation relationship exists, we will follow standard methodology by 1) establishing that there is an association between the causal variable (e.g. CBTi intervention) and the outcome (e.g. neurocognitive impairment), 2) establishing the association between the causal variable and the mediator and 3) showing that the mediator is associated with the outcome variable in a model with the causal variable included and 4) in the same model as used to evaluate step 3, determine that the relationship between the causal variable and the outcome variable is attenuated by inclusion of the mediator in the model. We do not expect to observe complete mediation in any of our investigations. Specifically, the above methodology will be used to test hypothesis 1.2.2.b with the causal variable defined as CBTi intervention, mediator as change in insomnia (ISI) and outcomes as neurocognitive indices. Hypothesis 1.2.2.c will consider change in insomnia as the causal variable, neurocognitive function indices, emotional distress symptoms and cardiovascular risk indices as mediators for the outcome HRQoL at 6 months. In addition to the stepwise model-based approach outlined above, we will also evaluate relationships using Structural Equation Modelling (SEM) approaches to evaluating mediation, which would allow simultaneous evaluation of the multiple pathways and classes of variables together in a single model, with improved power, allowing estimates of direct and indirect effects calculated from each. All effects size estimates (mean differences and/or odds ratios) will be presented along with associated confidence intervals and two-sided p-values, both unadjusted and adjusted for multiple comparisons. Primary therapies for childhood cancer have been associated with insomnia and study outcomes (neurocognitive morbidities, emotional distress, cardiovascular risk). Because our study inclusion criteria require that survivors have observed neurocognitive deficits we do not expect differential responses to SHUTi by previous childhood cancer treatment exposures. However, chemotherapy exposures and radiation doses are abstracted from medical records and cumulative doses of methotrexate (high dose and intrathecal), cytarabine, and cranial radiation will be included as covariates in relevant analyses. In addition, we will conduct sensitivity analyses to examine their contributions to treatment response.

We have planned for 20% attrition over the course of the 6-month study. However, if there is a substantial amount of missing data at 9 weeks or 6 months we will examine the characteristics of survivors who have complete data with those who do not. Depending upon the pattern of missing data, we will conduct sensitivity analyses to assess the impact of missing data on the results. We will consider factors such as demographic and treatment variables as well as premorbid baseline functioning in our sensitivity analyses.

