### **3.5. Procedures for Identifying and Randomizing Research Participants**

Prior to initiating the study, team members will be trained on the protocol and study procedures. The background to the study, study procedures, consent processes for the online or the verbal consent, data transfer, and plans to monitor intervention integrity and data quality will be part of the training.

[figure not shown]
Following the study preparation, initial screening for eligibility, consent and additional eligibility verification for the research participants will begin. Once consented and eligibility is confirmed, participants will be randomized using a permuted-block method with random block sizes, stratified on sex, age (<40 vs.  $\geq 40$ ), and cranial radiation therapy (Y/N). Following randomization, participants will complete the remote cognitive assessment, will provide a blood sample using the Dried Blood Spot (DBS) method and wear a WHOOP wrist monitor for 7 to 11 consecutive days. Following the remote evaluation, they will receive a direct link to access the SHUTi program or online patient education (per randomization).

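### Adjustment beyond the stratification factors depends on an undefined look at observed balance, so the primary ISI result is not tied to one model

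*Combined protocol and SAP*

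**What the plan says.** Section 9.1 (Statistical Analysis) opens with the balance rule: "Balance of patient characteristics between study arms will be evaluated and if necessary, adjusted comparisons will be carried out". The sentence comes before the primary-endpoint paragraph and is not limited to secondary endpoints.

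The next paragraph sets the primary model. Mean ISI change is "compared between study arms using linear regression (adjusted for stratification factors"), with 10 weeks as the primary time point and a two-sided 0.05 level. Section 3.5 gives the strata as sex, age (under 40 or not) and cranial radiation (yes/no). Baseline ISI enters only through the change score; it is not named as a covariate.

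Two further statements bear on the point:

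- On sex: "we plan to carry out all analyses and report results separately by sex". A combined analysis is considered only "if we deem that the effects are reasonably comparable between sexes".
- Later in the section, cumulative doses of methotrexate, cytarabine and "cranial radiation will be included as covariates in relevant analyses". Which analyses are relevant is not defined.

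**The concern.** After valid randomisation, any difference in baseline characteristics between arms is due to chance. A rule that reacts to such differences picks covariates for the size of the accident. What makes a covariate worth adjusting for is how well it predicts ISI change.

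The plan leaves open what is inspected, what counts as imbalance, when adjustment becomes necessary, and what standing the adjusted result has. Two results for the primary endpoint can therefore exist, one from the strata-adjusted model and one from the extended model, with no rule that says which is primary.

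Because the analyses are run by sex, the added covariates can also differ between women and men. The judgement about pooling would then compare estimates of unequal precision from differently built models. At stake are a modest inflation of the type I error if the choice is made freely, and precision that a fixed model would deliver.

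**Working it through.** **Inputs from the documents** (Section 9.1, Power and sample size): 80 per arm within each sex at the primary time point, about 70 per arm at 6 months, 160 per arm combined; 80% power; two-sided 0.05; stated detectable effects 0.45, 0.48 and 0.31. No SD, correlation or explained variance is given.

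**Step 1: reproduce the stated figures.** With no covariates, detectable effect = (1.960 + 0.842) × √(2/n).

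- n = 80: 2.802 × 0.1581 = 0.443 (stated 0.45)
- n = 70: 2.802 × 0.1690 = 0.474 (stated 0.48)
- n = 160: 2.802 × 0.1118 = 0.313 (stated 0.31)

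All three agree. Per-sex power at 0.45 is Φ(0.45/0.1581 − 1.960) = Φ(0.886) = 81.2%. Combined power at 0.31 is 79.2%. The plan takes no credit for covariates.

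**Step 2: could women and men receive different covariates?** Assume k independent characteristics, each tested at 0.05 within each sex. The plan states neither k nor a threshold. For one characteristic, both sexes agree with probability 0.05² + 0.95² = 0.905, so P(different sets) = 1 − 0.905^k. This gives 9.5% (k = 1), 39% (k = 5) and 63% (k = 10).

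**Step 3: size and power of a balance trigger.** Simulated at 80 per arm with a trigger at p < 0.05. The strata were left out, so the unadjusted or change-only model stands in for the strata-adjusted one.

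Baseline ISI as the only candidate covariate (40,000 trials per setting; ρ is the assumed baseline/post correlation, with equal SDs):

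| ρ | Size, triggered | Size, better of change-only and adjusted | Power at 0.45: change-only / triggered / always adjusted |
|---|---|---|---|
| 0.3 | 4.1% | 8.0% | 80.8 / 82.4 / 93.9% |
| 0.5 | 4.6% | 7.5% | 80.9 / 82.0 / 90.2% |
| 0.7 | 4.5% | 6.9% | 80.5 / 81.2 / 86.2% |

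The better-of-two column lets the analyst choose between the two models whatever the balance shows.

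With 10 or 15 covariates that together explain an assumed 20-30% of outcome variance, the mechanical trigger again has size of about 4-5% and power of 81-83%. The better of the unadjusted and triggered results has size 5.0-6.2%. The same covariates fixed in advance give 86-91% power. In one more extreme setting (a single covariate explaining 50%), the trigger's size fell to 3.5%.

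**Step 4: gain from fixing baseline ISI in the model.** The variance of the change score is 2(1 − ρ)σ². The residual variance after adjusting for baseline is (1 − ρ²)σ². Their ratio is (1 + ρ)/2. Taking 0.45 in SDs of change, power = Φ(0.45/(0.1581 × √ratio) − 1.960).

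- ρ = 0.3: ratio 0.65, power 94.2%
- ρ = 0.5: ratio 0.75, power 90.8%
- ρ = 0.7: ratio 0.85, power 87.0%

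Combined power at 0.31 rises from 79.2% to 93.0%, 89.3% and 85.3% respectively. The gain goes to zero if the slope of post on baseline ISI is 1.

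**Step 5: limits of the gain.** Fixing 10 or 15 weak covariates gives 80.4% or 78.6% power at R² = 0.05, and 82.9% or 81.2% at R² = 0.10, against about 81% unadjusted.

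**Step 6: does the covariate set change the target?** With a true effect of 0.45, the unadjusted, triggered and fully adjusted estimates all averaged 0.448-0.452. Precision differs; the effect being estimated does not.

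**The case against.** The plan does pre-specify a primary model, adjusted for the strata, at a stated time point and level. Nothing says that the conditional comparison would replace it, and the sentence can be read as describing a supportive analysis. The dose covariates are a partial fixed list. The documents contain no 0.05 balance test, no number of characteristics and no statement that balance is checked within sex; these are assumptions made to size the problem. Followed mechanically, the rule does not inflate error, and the inflated figures require someone to pick the better result, which the plan does not propose.

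Most of this stands, and it rules out three stronger readings that a reader might infer:

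- That all covariate adjustment is balance-driven. It is not; the strata are always in the model.
- That the trial loses its planned power. It does not; the stated effects reproduce without covariates, and the trigger is marginally above the change-only model.
- That different covariates make the estimates for women and men non-comparable. In a linear model of a randomised mean difference both target the same effect (Step 6).

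What remains is that the plan's silence on criterion, list and status leaves the choice open. The dose covariates do not close it, because the analyses they apply to are undefined.

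**Conclusion.** The point holds in a limited form. Adjustment beyond the strata is left to an undefined, post-allocation look at balance, so two candidate primary results can exist and their covariates can differ by sex. The size of a mechanical rule is about 4-5%. Free choice of the better model gives about 5-6%, or 7-8% where baseline ISI is the covariate in question. The precision forgone is the gap between about 81-82% and 87-94% per-sex power. That gap rests on an assumed correlation of 0.7 to 0.3 with equal SDs, neither of which is in the documents, and it shrinks or disappears with weakly prognostic covariates. This should be changed, but it does not undermine the design or the stated power.

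**What to change.** In Section 9.1, delete the conditional half of the balance sentence. State one primary model: linear regression of ISI change on arm, the stratification factors and baseline (pre-intervention) ISI, plus at most a few named prognostic variables held before randomisation. Say explicitly whether the treatment-dose covariates belong to it. Use the same list in women, in men (sex dropping out within sex) and in any combined model, whatever the balance looks like. Present baseline characteristics by arm descriptively, without tests, and label any imbalance-driven model as a sensitivity analysis.

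One detail needs settling. Section 3.5 places the baseline remote evaluation after randomisation and before programme access. The plan should therefore say when the baseline ISI is taken and that this precedes knowledge of the arm. The ISI collected for eligibility under Section 3.1.3 is available before randomisation if that cannot be assured.

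The cost is wording only, with no new data or procedures. The downside is that the list must be agreed before outcomes are seen by arm.
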